9. RESEARCH METHODS

9.1. Study Design

This is an observational, non-interventional, prospective, multicenter and nationwide study with the category of PASS (Post Authorization Safety Study), which seeks to answer the research question: what is the spectrum of adverse events and mitigation strategies associated with lorlatinib in a real-world Spanish population? For this purpose, an observational, non-interventional and prospective study design is ideal to faithfully reflect what occurs in the routine clinical practice.

It is important to note that our study population exhibits a low incidence of NSCLC patients, approximately 3-4%. Consequently, the current study is descriptive in nature, as it lacks the statistical robustness (relatively small sample, but almost similar to the total of patients included in the pivotal trial) necessary to establish a significant association between a specific adverse event and the drug.

The primary objective will be to describe all the spectrum of the AEs of Iorlatinib (CTCAE v6.0) and its mitigation strategies with special interest in CNS AEs.

Primary Objective	Corresponding Endpoint			
To describe all the spectrum of the adverse events (AEs) of Lorlatinib (CTCAE v6.0) and its mitigation strategies, with special interest in CNS AEs	Occurrence (number of adverse events) and severity of AEs, with severity determined according to NCI CTCAE v6.0 criteria. Frequency and period of dose reductions as well as concurrent medications used to control AEs will be collected			
Secondary Objectives	Corresponding Endpoints			
To identify factors that are predictive of AEs, with special interest in CNS AEs	To evaluate the relationship of multiple demographic and clinical factors with the incidence of AEs, with special interest in CNS adverse events			
To evaluate the effectiveness of 1L lorlatinib in real-world practice	• Effectiveness will be assessed:			
rwPFS rate at 12 and 18 months in the ITT population with and without brain metastasis at baseline	1. To determine real-world progression-free survival (rwPFS) defined as the time from enrollment to the first occurrence of disease progression (intracranial or systemic) or death from any cause, whichever occurs first, as determined by the investigator using RECIST v1.1. criteria, at 12 and 18 months, in the ITT population with and without brain metastasis at baseline			

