- 1. **Baseline visit:** the day on which the patient fulfils the inclusion and exclusion criterion, including signature of the Informed Consent (i.e. the day on which the prospective observation starts) (within cycle 1 if lorlatinib)
- 2. Follow-up visit 1: will be scheduled at month 3 (third cycle of Iorlatinib)
- 3. Follow-up visit 2: will be scheduled at month 6 (sixth cycle of Iorlatinib)
- 4. Follow-up visit 3: Follow-up visit at month 12 (twelfth cycle of lorlatinib)
- 5. Final Visit: end of follow-up (end of data collection expected November 2027)

Data collection overview

Study Visits and Assessments	Baseline			FU3 C12D1	Final Visit
Informed consent	X				
SOCIO DEMOGRAPHIC DATA					
Medical history	X				
Physical examination including Height and weight	X	X	X	X	X

Study Visits and Assessments	Baseline	FU1	FU2	FU3	Final
		C3D1	C6D1	C12D1	Visit
Previous personal and family history of cancer	X				
CLINICAL DATA					
ECOG	X	X	X	X	X
Laboratory: Hematology and Blood chemistry (dyslipemia profile included). According to routine clinical practice	X	X	X	X	X
Comorbidities since Index Date: Charlson Index	X	X	X	X	X
Concomitant treatment(s) including previous history of Thromboembolic Disease	X	Х	X	X	X
Information of baseline tumor diagnosis: date, staging, (TNM),biopsy, PD-L1 expression, other mutations, etc	X				
Information regarding advanced disease: date, staging, metastatic location, CNS metastasis, previous systemic chemotherapy, radiotherapy, etc	X				
Previous systemic chemotherapy (Yes/No)	X				
Assessments CT scan	X				
Assessments brain MRI	X				
LORLATINIB TREATMENT					
Start, Stop and Discontinuation date	X	X	X	X	X
Dose by cycle	X	X	X	X	X
Reason for discontinuation or for dose reduction	X	X	X	X	X
Evaluation of Treatment Response: method (CT scan, MRI, others) and response	х	Х	X	X	X
AFTER LORLATINIB TREATMENT					

Study Visits and Assessments		FU1	FU2	FU3	Final
		C3D1	C6D1	C12D1	Visit
Post-progression treatment: type and palliative care					X
Date of death or last follow-up or last contact					X
QUALITY OF LIVE					
EORTC QLQ C30, LC13	X	X	X	X	X
SAFETY					
PRO-CTCAE	X	X	X	X	X
Adverse Events	X	X	X	X	X

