Most often, the date of informed consent is the same as the date of enrollment. In some situations, there may be a lag between the dates of informed consent and enrollment. In these instances, if a patient provides informed consent but is never enrolled in the study (eg, patient changes his/her mind about participation, the reporting period ends on the date of the decision to not enroll the patient.

If the investigator becomes aware of an SAE occurring at any time after completion of the study and s/he considers the SAE to be related to lorlatinib, the SAE also must be reported to Pfizer DSU.

DEFINITIONS OF SAFETY EVENTS

Adverse events

An AE is any untoward medical occurrence in a patient administered a medicinal product. The event need not necessarily have a causal relationship with the product treatment or usage. Examples of AEs include but are not limited to:

- Abnormal test findings (see below for circumstances in which an abnormal test finding constitutes an AE)
- Clinically significant signs and symptoms
- Changes in physical examination findings
- Hypersensitivity
- Lack of efficacy
- Drug abuse

PFIZER CONFIDENTIAL

Drug dependency

Additionally, for medicinal products, they may include the signs or symptoms resulting from:

- Drug overdose
- Drug withdrawal
- Drug misuse
- Off-label use
- Drug interactions
- Extravasation
- Exposure during pregnancy
- Exposure during breastfeeding
- Medication error
- Occupational exposure

Abnormal test findings

The criteria for determining whether an abnormal objective test finding should be reported as an AE are as follows:

- Test result is associated with accompanying symptoms.
- Test result requires additional diagnostic testing or medical/surgical intervention.
- Test result leads to a change in study dosing or discontinuation from the study, significant additional concomitant drug treatment, or other therapy.
- Test result is considered to be an AE by the investigator or Sponsor.

Merely repeating an abnormal test, in the absence of any of the above conditions, does not constitute an AE. Any abnormal test result that is determined to be an error does not require reporting as an AE.

Serious adverse events

An SAE is any untoward medical occurrence in a patient administered a medicinal or nutritional product (including pediatric formulas) at any dose that:

- Results in death
- Is life-threatening

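### The rule that turns laboratory results into AEs has no grade threshold and depends partly on action taken, so lipid AE incidence may be understated and any mitigated share overstated

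*Protocol*

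**What the plan says.** Section 9.1 of the protocol sets the primary endpoint in two parts. The first is "Occurrence (number of adverse events) and severity of AEs, with severity determined according to NCI CTCAE v6.0 criteria". The second covers mitigation: "Frequency and period of dose reductions as well as concurrent medications used to control AEs will be collected".

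Section 11, under abnormal test findings, gives four criteria for reporting an abnormal objective test as an AE. They are read here as alternatives:

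1. "Test result is associated with accompanying symptoms"
2. "Test result requires additional diagnostic testing or medical/surgical intervention"
3. "Test result leads to a change in study dosing or discontinuation from the study, significant additional concomitant drug treatment, or other therapy"
4. "Test result is considered to be an AE by the investigator or Sponsor"

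It adds: "Merely repeating an abnormal test, in the absence of any of the above conditions, does not constitute an AE". None of the criteria refers to a CTCAE grade.

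The data collection overview in Section 9.2 schedules, at baseline, the three follow-up visits and the final visit: "Laboratory: Hematology and Blood chemistry (dyslipemia profile included). According to routine clinical practice". The variable table in Section 9.3 lists no haematology or chemistry values.

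The abstract and Section 7 name hyperlipidaemia, weight gain and hypertension as the most common grade 3/4 events. Section 7 gives pivotal-trial grade 3/4 rates on lorlatinib of 25% for hypertriglyceridaemia, 21% for hypercholesterolaemia, 23% for weight gain and 12% for hypertension.

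**The concern.** Raised lipids are largely a laboratory finding. Under Section 11, a rise without symptoms becomes an AE because it needed work-up or intervention, because it led to a dose change or drug, or because someone chose to call it one. Dose reductions and concurrent drugs are also what the primary endpoint collects as mitigation, so the outcome being described helps to decide which events are counted.

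Two results are exposed. First, the frequency and grade distribution of lipid AEs would partly reflect each site's threshold for acting, across about 20 sites. Second, if mitigation is reported as a percentage of lipid AEs, untreated cases that were never recorded are missing from the denominator and the percentage rises.

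There are knock-on effects. Section 9.7 also reports each AE relative to all reported AEs, so missing lipid events shift the shares of other AEs, including CNS AEs. The secondary objective on predictors of AEs could, for laboratory events, pick up predictors of being treated.

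**Working it through.** The protocol states no figure on this point, so there is none to reproduce. The check is of the mechanism and its direction.

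**Which lipid rises enter the endpoint**

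- With symptoms: criterion 1.
- Without symptoms, needing further testing or intervention: criterion 2.
- Without symptoms, leading to a dose change, discontinuation or added therapy: criterion 3.
- Without symptoms and none of these: criterion 4 only, with no grade to guide it.

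**Inputs**

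- N = 116, the planned size (Section 9.5), used only to scale the result.
- T = true share of patients with a CTCAE-gradable lipid rise. Assumed.
- a = share of those who are acted on. Assumed.
- q = chance that a rise not acted on is still recorded under criterion 4. Assumed.

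Symptom-only cases and cases with further testing only are ignored for simplicity. Both would be recorded without mitigation, so they soften the effect.

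**Formulas**

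- Recorded incidence = T × [a + (1 − a)q]
- Mitigated share among recorded cases = a / [a + (1 − a)q]

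The bracket is below 1 whenever a < 1 and q < 1. Recorded incidence is then below T and the apparent mitigated share is above a. The direction is fixed; the size is not.

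**Results with T = 0.80** (true count 0.80 × 116 = 92.8, about 93)

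| a | q | Recorded incidence | Patients of 116 | Apparent mitigated share |
|---|---|---|---|---|
| 0.30 | 0 | 0.24 | 28 | 100% |
| 0.30 | 0.5 | 0.52 | 60 | 46% |
| 0.30 | 1 | 0.80 | 93 | 30% |
| 0.50 | 0 | 0.40 | 46 | 100% |
| 0.50 | 0.25 | 0.50 | 58 | 80% |
| 0.50 | 0.5 | 0.60 | 70 | 67% |
| 0.50 | 1 | 0.80 | 93 | 50% |
| 0.70 | 0 | 0.56 | 65 | 100% |
| 0.70 | 0.5 | 0.68 | 79 | 82% |
| 0.70 | 1 | 0.80 | 93 | 70% |
| 0.90 | 0 | 0.72 | 84 | 100% |
| 0.90 | 0.5 | 0.76 | 88 | 95% |
| 0.90 | 1 | 0.80 | 93 | 90% |

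Worked line: a = 0.50, q = 0.5 gives 0.80 × (0.50 + 0.50 × 0.5) = 0.60, and 0.60 × 116 = 69.6, about 70. The mitigated share is 0.50 / 0.75 = 67%, against a true 50%.

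**Range.** Let T run from 0.60 to 0.90 and a from 0.40 to 0.90.

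- q = 0: recorded incidence runs from 0.60 × 0.40 = 24% to 0.90 × 0.90 = 81%.
- q = 0.5: it runs from 0.60 × 0.70 = 42% to 0.90 × 0.95 = 85.5%.

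Much of that spread is T itself and is not bias. The fraction of true cases captured isolates the bias. It is the bracket alone: 40% to 90% at q = 0, and 70% to 95% at q = 0.5.

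**The case against.** **The criteria are alternatives, and criterion 4 is open.** Any lipid result may be recorded under it. Criterion 1 admits events without mitigation, as does the further-testing limb of criterion 2. Criterion 2 also speaks of what a result requires, so a value judged to need treatment but left untreated qualifies. All of this stands. A reader might infer that recorded lipid AEs will almost always be mitigated by construction; the text does not support that. It would follow only if discretionary reporting were near zero or nearly every case were treated anyway. The loss is confined to asymptomatic rises that are not acted on, probably of lower grade.

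**No mitigated-share denominator is stated.** Section 9.1 says only that dose reductions and medications will be collected, and Section 9.7 reports AEs over all patients. This stands too. The overstatement applies to a percentage among lipid AEs, if one is reported. The understatement of incidence does not depend on it.

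**Hyperlipidaemia is not shown to be the commonest toxicity.** It is listed beside weight gain and hypertension, for grade 3/4 only. The stated special interest and the sample size concern CNS AEs. The point is therefore limited to a leading laboratory toxicity and does not reach the whole primary objective.

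**CTCAE grading of laboratory values could be set in the SAP.** This is partly right, since Section 9.7 assigns outcome definitions and table shells there. But the AE rule and the data to be captured are protocol content. Values are scheduled in Section 9.2 and absent from the list in Section 9.3. If numeric results do not reach the eCRF, no SAP can grade them. Section 9.7 also says that major changes to primary endpoint definitions or their analyses would be reflected in a protocol amendment.

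**Routine testing frequency still varies by site.** True; the fix reduces the dependence on action and leaves the dependence on testing.

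**Conclusion.** The point holds in a limited form. Section 11 has no grade threshold for laboratory AEs and relies in part on the same actions that the primary endpoint counts as mitigation. Asymptomatic, untreated lipid rises are counted at each site's discretion. Whenever that discretion is used incompletely and not every case is acted on, lipid AE incidence is understated and any mitigated proportion among those AEs is overstated.

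The direction follows from the text. The size cannot be derived from it, because the protocol gives no any-grade lipid rate, no treated share and no rate of discretionary reporting. The illustration rests wholly on assumed values of these three. It runs from no distortion (every untreated case reported, or every case treated) to losing 60% of true cases (40% acted on, none of the rest reported). This is a worthwhile, inexpensive improvement to how the primary objective is answered for one leading toxicity class. It does not invalidate the study.

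**What to change.** 1. Section 9.3: add dated laboratory values to the variable list, at least cholesterol and triglycerides, from the tests already scheduled in Section 9.2.
2. Section 9.7: state that laboratory toxicities will also be graded by CTCAE v6.0 from the collected values, whether or not action was taken, with incidence and worst grade reported on that basis.
3. Section 9.7: state that any mitigation percentage for these toxicities uses all laboratory-graded patients as denominator.
4. Section 11: keep the existing rule for AE and safety reporting.

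The cost is a few eCRF fields and one extra table. Reported any-grade laboratory rates will be higher than under AE reporting alone, which the report should explain. The results will still depend on how often each site tests in routine practice.

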radiotherapy, presence/absence of baseline intracranial metastasis, use of concomitant drugs, or personal clinical history of psychiatric/mood diseases⁶. However, limited data are available about the occurrence of CNS AEs when lorlatinib is used in the first line of treatment (local approval in Spain February 2023) in a real-world population.

On the other hand, lorlatinib has proved its efficacy and safety in clinical trials, but real-world evidence is needed to confirm these results in wider patient populations and to identify prognostic and predictive factors not captured in clinical trials. Ethnicity, molecular variants, and circulating tumour DNA (ctDNA) clearance may influence treatment outcomes and require personalized or combinational approaches.

Research question and objectives

Research question

 What is the spectrum of adverse events and mitigation strategies associated with lorlatinib as a first line treatment in an ALK+ NSCLC real-world Spanish population?

Primary Objective

 To describe all the spectrum of the adverse events (AEs) of Lorlatinib (CTCAE v6.0) and its mitigation strategies, with special interest in CNS AEs

Secondary Objectives

- To identify factors that are predictive of AEs, with special interest in CNS AEs
- To evaluate the effectiveness of 1L lorlatinib in real-world practice
 - 1. rwPFS rate at 12 and 18 months in the ITT population with and without brain metastasis at baseline
 - 2. rwDuration of Response (DoR)
 - 3. rwDuration of Treatment (DoT)
 - 4. rwTime to next therapy/treatment (TTNT)
 - 5. rwSystemic and intracranial Objective Response rate (ORR) using Response Evaluation Criteria in Solid Tumors (RECIST) v1.1. criteria
 - 6. rwTime to intracranial progression rate at 12 and 18 months with and without brain metastasis at baseline
 - 7. rwCumulative incidence of brain metastases (BM) in ITT population at 12 and 18 months (with and without baseline BM)

- 8. rwOverall survival (OS) rate at 12 and 18m
- To evaluate the impact of lorlatinib on patients' quality of life
- To describe ALK testing methods used

Exploratory Objectives (up to 30 patients)

 To identify neuroimaging markers (Magnetic Resonance Imaging; MRI) that are predictive of the occurrence of CNS AEs

Study Design

The study is an observational, non-interventional, prospective and multicenter trial that evaluates the real-world safety and effectiveness of lorlatinib as a first-line treatment in patients with ALK-positive advanced NSCLC in Spain.

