Only variables obtained according to routine clinical practice that follow objectives can and should be documented in this study and follow objectives.

To describe the safety profile of lorlatinib in the patients under the study, the following variables will be collected:

- AE, serious adverse events (SAE), and treatment-associated mortality.
- Time to onset and duration of AEs

Adverse events included in the study database will be coded according to CTCAE v6.0.

To study the safety profile, all adverse events that have been identified since the start of treatment with lorlatinib and related to the drug will be collected in the CRF. (More detail in section 11).

Researchers are reminded of their obligation to notify adverse reactions that the Pharmacovigilance Center as they are aware of.

Quality of Life (QoL) Assessments

Scales will be completed by patients at each study visit:

- EORTC QLQ C30: is a cancer-specific quality of life questionnaire (QLQ-C30), which consists of five functional scales (physical, role, cognitive, emotional, and social); nine symptom scales (fatigue, pain, nausea and vomiting, dyspnea, loss of appetite, insomnia, constipation, diarrhea, and financial difficulties); and a global health status/quality of life (GHS/QoL). Based on 30 questions in total, the scores range from 0 to 100. This questionnaire was approved and psychometrically validated (as well as each of its translations).
- QLQ LC13: the EORTC QLQ-LC13 is a supplementary questionnaire specifically designed for lung cancer patients. It is used in conjunction with the EORTC QLQ-C30 to assess the quality of life in these patients. The QLQ-LC13 focuses on lung cancer-specific symptoms and treatment side effects, such as coughing, shortness of breath, pain, and side effects from chemotherapy¹⁰.

• PRO-CTCAE (for CNS AEs)¹¹: is a tool developed by the National Cancer Institute (NCI) to capture symptomatic adverse events directly from patients receiving cancer treatment. It includes a set of questions that patients can answer to report the severity, frequency, and interference of symptoms they experience. When referring to CNS (Central Nervous System) adverse events, the PRO-CTCAE helps in assessing symptoms such as headaches, dizziness, and cognitive changes, which are crucial for understanding the impact of cancer treatments on the nervous system.

Exploratory variables (30 patients expected)

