- Requires inpatient hospitalization or prolongation of hospitalization (see below for circumstances that do not constitute SAEs)
- Results in persistent or significant disability/incapacity (substantial disruption of the ability to conduct normal life functions)
- Results in congenital anomaly/birth defect

Since progression of underlying malignancy is being assessed as an efficacy variable, it should not be reported as an AE or SAE. The terms "Disease Progression", "Progression of Disease", or "Malignant disease progression" and other similar terms should not be used to describe an AE or SAE. However, clinical symptoms of progression may be reported as AEs or SAEs if the symptom cannot be determined as exclusively due to progression of the underlying malignancy or does not fit the expected pattern of progression for the disease under study. In addition, complications from progression of the underlying malignancy should be recorded as AEs or as SAEs in CRF.

Important Medical Event

Medical and scientific judgment is exercised in determining whether an event is an important medical event. An important medical event may not be immediately life-threatening and/or result in death or hospitalization. However, if it is determined that the event may jeopardize the patient or may require intervention to prevent one of the other outcomes listed in the definition above, the important medical event should be reported as serious.

Examples of such events are intensive treatment in an emergency room or at home for allergic bronchospasm; blood dyscrasias or convulsions that do not result in hospitalization; or development of drug dependency or drug abuse.

Suspected Transmission of an Infectious Agent

Additionally, any suspected transmission via lorlatinib of an infectious agent, pathogenic or non-pathogenic, is considered serious. The event may be suspected from clinical symptoms or laboratory findings indicating an infection in a patient exposed to lorlatinib. The terms "suspected transmission" and "transmission" are considered synonymous. These cases are considered unexpected and handled as serious expedited cases by pharmacovigilance (PV) personnel. Such cases are also considered for reporting as product defects, if appropriate.

Hospitalization

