Hospitalization is defined as any initial admission (even if less than 24 hours) to a hospital or equivalent healthcare facility or any prolongation to an existing admission. Admission also includes transfer within the hospital to an acute/intensive care unit (eg, from the psychiatric wing to a medical floor, medical floor to a coronary care unit, neurological floor to a tuberculosis unit). An emergency room visit does not necessarily constitute a hospitalization; however, an event leading to an emergency room visit should be assessed for medical importance.

Hospitalization in the absence of a medical AE is not in itself an AE and is not reportable. For example, the following reports of hospitalization without a medical AE are not to be reported:

- Social admission (eg, patient has no place to sleep)
- Administrative admission (eg, for yearly exam)
- Optional admission not associated with a precipitating medical AE (eg, for elective cosmetic surgery)

PFIZER CONFIDENTIAL

- Hospitalization for observation without a medical AE
- Admission for treatment of a pre-existing condition not associated with the development of a new AE or with a worsening of the pre-existing condition (eg, for work-up of persistent pre treatment lab abnormality)

Causality assessment

The investigator is required to assess and record the causal relationship.

An investigator's causality assessment is the determination of whether there exists a reasonable possibility that lorlatinib caused or contributed to the safety event. For all safety events, sufficient information should be obtained by the investigator to determine the causality.

If the investigator's final determination of causality is "unknown" and s/he cannot determine whether lorlatinib caused the event, the safety event must be reported per the process outlined in Table 6.

If the investigator cannot determine the etiology of the event but s/he determines that lorlatinib did not cause the event, this should be clearly documented on the CRF and the NIS AEM Report Form.

Endpoint Adjudication Committee

Not applicable

Exposure During Pregnancy, Exposure During Breastfeeding, Environmental Exposure and Occupational Exposure

Exposure during pregnancy

Prospective and retrospective exposure during pregnancy (EDP) reports are reportable using the NIS AEM Report Form and the EDP Supplemental Form, irrespective of the presence of an associated safety event.

The procedures for reporting as per Table 6 should be followed.

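### The protocol does not fix whether CNS AEs include neurological complications of brain progression, and sections 9.3 and 11 disagree on which AEs the CRF holds

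*Protocol*

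**What the plan says.** **What enters the AE data.** Under Serious adverse events, section 11 states: "Since progression of underlying malignancy is being assessed as an efficacy variable, it should not be reported as an AE or SAE". Clinical symptoms of progression may be reported "if the symptom cannot be determined as exclusively due to progression of the underlying malignancy", or if they fall outside the expected pattern for the disease. It then adds that "complications from progression of the underlying malignancy should be recorded as AEs or as SAEs in CRF". No line is drawn between a symptom and a complication. Table 6 requires all serious and non-serious AEs on the CRF. The text after it makes reporting independent of relatedness, and the AE definition needs no causal link.

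**The competing rule.** The text after the variables table in section 9.3 says that AEs identified since the start of lorlatinib and "related to the drug will be collected in the CRF", and refers to section 11 for detail.

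**How the events are used.** The first secondary endpoint in section 9.1 is "To evaluate the relationship of multiple demographic and clinical factors with the incidence of AEs, with special interest in CNS adverse events". Section 9.7 summarises the frequency and severity of AEs with no split by cause. Section 9.5 sizes the study on CNS AEs of any grade. The protocol does not define a CNS AE, and endpoint adjudication is marked as not applicable.

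**The candidate predictors.** The abstract lists prior brain radiotherapy and "presence/absence of baseline intracranial metastasis" among factors linked to CNS AEs in previously treated patients. Section 9.3 collects both at baseline.

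**What could separate the events.** Under Causality assessment, section 11 states: "The investigator is required to assess and record the causal relationship". If the cause is unclear but lorlatinib is ruled out, "this should be clearly documented on the CRF and the NIS AEM Report Form". Section 9.3 also collects brain progression (Yes/No), progression location, one date of progression, and time to onset of AEs.

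**The concern.** CNS AEs are the events of special interest in the primary objective and in the first secondary objective. Confusion, mood change or a speech deficit can come from the drug or from a growing brain metastasis. If tumour complications are counted, the outcome is no longer toxicity alone. Patients with baseline brain metastases or prior brain radiotherapy are plausibly those most exposed to such complications, so predictor and outcome can become linked through the tumour. A positive association could then appear with no difference in drug toxicity, and be read as a reason for caution in patients for whom intracranial activity matters most.

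The conflict over what the CRF holds adds a second problem. A site following section 9.3 may leave out events that a site following section 11 records, so the count may depend on which section a site reads.

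**Working it through.** **1. The plan's own figure.** Inputs from section 9.5: reference incidence 42%, target 55%, 80% power, two-sided test. Alpha is not stated, so 0.05 is assumed. One-sample normal approximation:

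n = [(1.960·√(0.42·0.58) + 0.842·√(0.55·0.45)) / 0.13]² = 113.7, so 114.

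The arcsine form gives 115.3, so 116. The stated 116 is reproduced and is not in dispute. The 42% is used below as the starting rate.

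**2. The recording rules side by side.**

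| Place | AEs on the CRF |
|---|---|
| Section 9.3, text after the table | Those related to the drug |
| Section 11, Table 6 | All |
| Section 11, text after Table 6 | Reporting as per Table 6, regardless of relatedness |
| Section 11, Serious adverse events | Includes complications of progression |

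The first row cannot be followed together with the others.

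**3. Illustration of the bias.** The documents give no rate of neurological complications of progression, so these inputs are assumptions:
- Drug-caused CNS AE risk is 42% in every patient. The protocol gives 42% only as an incidence, not as drug-caused.
- The share with baseline brain metastases (BM) is 35/149 = 23.5%, from the pivotal-trial lorlatinib figures in section 7. This gives about 27 of 116 patients, and 89 without.
- Complications occur independently of drug effects, with risk q, and all-cause events are analysed.

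Observed rate = 1 − (1 − 0.42)(1 − q) = 0.42 + 0.58q.

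| q with BM | q without BM | Rate with BM | Rate without BM | Odds ratio | Overall |
|---|---|---|---|---|---|
| 5% | 1% | 44.9% | 42.6% | 1.10 | 43.1% |
| 10% | 2% | 47.8% | 43.2% | 1.21 | 44.2% |
| 20% | 3% | 53.6% | 43.7% | 1.49 | 46.1% |
| 20% | 20% | 53.6% | 53.6% | 1.00 | 53.6% |

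The last row is a boundary case showing that the odds ratio is unaffected when risks are equal. It is not offered as a plausible incidence: section 7 puts progression at any site at 20% in the first 12 months of the pivotal trial.

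If only related events are analysed and every attribution is correct, the odds ratio is 1.00 throughout.

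**4. Scale against sampling error.** The 95% half-width for an incidence of 42% with 116 patients is 1.96·√(0.42·0.58/116) = 0.090. The shift of 1 to 4 points in the first three rows is well inside it. For the odds ratio in the third row, the expected counts are about 14.5/12.5 and 38.9/50.1. The standard error of the log odds ratio is √(1/14.5 + 1/12.5 + 1/38.9 + 1/50.1) = 0.44. The bias is ln 1.49 = 0.40, about 0.9 of a standard error.

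**5. Can the planned variables separate the events?** Only in part.
- The causality question asks whether lorlatinib had a causal or contributory role. For confusion in a patient with brain progression, the answer can be yes while the tumour's role goes unrecorded.
- Brain progression is listed as Yes/No, with one general progression date and none of its own. Section 10.3 allows treatment beyond radiological progression in some circumstances. A brain progression that follows an extracranial one may therefore not be datable against the onset of an AE.

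**The case against.** A reader might infer that nothing in the protocol separates tumour complications from drug effects, so that these complications are bound to count as lorlatinib CNS AEs and baseline brain metastases are bound to appear predictive. The documents do not support that. Progression itself is excluded, and symptoms exclusively due to progression are in general kept out. Causality is recorded for every safety event. Brain progression, its location, a progression date and AE onset are collected. Brain MRI is collected in case of CNS toxicity where routine care provides it. Much of the overlap can be derived from these data.

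Three further points carry weight:
- Section 9.7 leaves the definition of outcomes to the SAP, which may choose related events.
- Section 9.1 speaks only of multiple demographic and clinical factors. The brain-metastasis and radiotherapy factors come from the background text, and no predictor model is specified.
- All-cause recording fits a primary objective that covers the whole range of AEs, and it should stay.

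It is also fair that the complication risks are assumed. Setting the risk to zero in patients without baseline brain metastases would inflate the odds ratio, and the protocol itself plans to measure brain metastases in that group.

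What remains is more than a detail for the SAP. The conflict between sections 9.3 and 11 concerns what sites enter, and the missing link between a CNS AE and intracranial progression concerns what is collected. Analysis cannot recover either afterwards. The MRI collection fills the gap only partly: it belongs to an exploratory objective of up to 30 patients, and its stated purposes are the Fazekas scale, morphometry and radiomics.

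**Conclusion.** The point holds in a limited form. The protocol contradicts itself on whether the CRF holds all AEs or only drug-related ones. If sections 9.1, 9.7 and 11 are followed as written, neurological complications of brain progression can enter the CNS AE count. This can bias an association with baseline brain metastases or prior brain radiotherapy upward, provided that those patients have more such complications and that all-cause events are analysed.

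The size of the bias cannot be derived from the documents. The illustrative odds ratios of about 1.1 to 1.5 rest on assumed complication risks, a common 42% drug-caused rate and independence. In those same scenarios the overall incidence rises by only 1 to 4 points, so the predictor objective is the part at risk.

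**What to change.** 1. Reconcile the section 9.3 text with Table 6, the text after it and the Serious adverse events text in section 11, so that all AEs are recorded on the CRF whatever their cause.
2. Add one eCRF item for each CNS AE: intracranial progression present or diagnosed around onset (Yes / No / Not assessed).
3. In section 9.7, keep the all-cause CNS AE incidence and show beside it the incidence of CNS AEs not attributed to intracranial progression, using the new item together with the causality already recorded.
4. Use the second count for the predictor analysis, with the all-cause result as a sensitivity analysis.

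The cost is one eCRF item, one extra table row and one repeated model. Attribution is partly a matter of judgement, and showing both counts lets the reader see how much depends on it. Safety reporting under section 11 is unchanged. The first two steps have to be made at data collection. Section 9.7 sends major modifications of primary endpoint definitions to a protocol amendment, so the protocol is a proper place to settle this.
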